Modulating interaction of motor learning networks in rehabilitation of stroke

NCT03086551

January 10th, 2018

SPECIFIC AIMS

Aim 1: Determine whether cTBS over contralesional dorsolateral prefrontal cortex prior to motor practice enhances motor learning post-stroke. Aim 1 will compare the efficacy of contralesional cTBS over dorsolateral prefrontal cortex paired with motor practice versus sham cTBS paired with practice for improving motor function.

Aim 2: Determine the effects of cTBS over dorsolateral prefrontal cortex upon motor networks. Our second aim is to determine the effect of our cTBS intervention upon local intracortical networks within primary motor cortex and across the motor network.

Aim 3: Provide preliminary evidence for individual predictors of the efficacy of dorsolateral prefrontal cortex cTBS post-stroke. Within our exploratory third aim, we will examine the relationship between pre-intervention behavioral and brain metrics and the responsiveness to dorsolateral prefrontal cortex cTBS.

RESEARCH STRATEGY

Design

Aims 1, 2 and 3 will be assessed in a single experiment. 16 individuals with first time middle cerebral artery (MCA) territory ischemic stroke will serve as their own matched control in a cross-over design. Each arm of the cross-over design will include the same 6 sessions (Figure 1). Each session within an arm of the cross-over design will be separated by at least 24 hours and the duration of each arm will not exceed three weeks. The only difference between the arms of the study will be the delivery active cTBS or sham cTBS over dorsolateral prefrontal cortex. The order of each arm will be counterbalanced. The four-session duration of the proposed intervention was informed by our past work pairing sensorimotor cortical stimulation with the same serial targeting task to be employed here. A three-week break between study arms will be employed to minimize carry over effects between each arm of the study. Therefore, total duration of the study from enrollment to completion

[figure not shown]

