Prior to each arm of the cross-over design patients will be informed of a repeated sequence of six targets that they will be required to reach to. Different sequences matched for difficulty will be used in each arm. Free recall will be performed prior to each session to assess any change in declarative knowledge.

During Sessions 2, 3, 4 and 5 of each cross-over arm participants will complete 30 reaches where the targets will occur in a random series. Participants will then complete a block of 60 reaches where the 6-element sequence will repeat 10 times. An additional block of 30 random reaches will then be completed. The pre-stimulation reaches will be used to assess sustained change in performance from session to session. This same set of 120 reaches will also be performed during Session 6 as a retention test.

For Sessions 2, 3, 4 & 5 participants will receive either active or sham cTBS over dorsolateral prefrontal cortex following the initial set of 120 reaches. Post-stimulation

[figure not shown]

Figure 2 – Serial Targeting task. Participants will be seated in front of a touch screen angled on a desk in front of them and be asked to touch sequentially presented targets using their paretic limb. Targets will be presented sequentially at one of nine locations (inset bottom left).

Study Title: Modulating interaction of motor learning networks in rehabilitation of stroke

participants will complete an additional 270 targeted reaches comprised solely of the 6-element repeating sequence.

The primary dependent measure for Aim 1 will be total response time to complete the sequence. As patients must stop within the target this metric captures both speed and accuracy. Comparison of response times during random reaches across session will be used to index sensorimotor procedural knowledge. Comparison of the difference between repeated and random reach response times will be used to index development of procedural knowledge relating to a larger sequence of movements.

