Functional Assessment of the Paretic Limb: As secondary measures, the modified *Jebsen-Hand Function Test* and the *Box and Blocks* will be used to assess change in functional motor ability. The Jebsen-Hand Function Test is a valid and reliable test of hand function in healthy and individuals post-stroke and shows good responsiveness in chronic stroke to non-invasive brain stimulation interventions. We will employ a commonly used subset of the Jebsen-Hand Function Test: turning over cards, putting small objects in a can, mimicked spoon feeding, stacking checkers and moving weighted cans. To minimize learning effects each item will be tested 5 times but only the last two times will be used to quantify ability at each assessment. Scores for the paretic limb will be normalized to those of the non-paretic limb. The Box and Blocks test is a valid and reliable measure of gross manual dexterity. The Box and Blocks tests involves moving as many blocks from one side of a compartment over a partition to the other side in a 60-s window. The test is performed for both the paretic and non-paretic limb.

Attention, Spatial Working Memory, Verbal Working Memory: To comprehensively characterize our stroke groups we will use the Trail Making test to categorize visuomotor tracking and divided attention abilities. Where applicable, all participants will respond using their non-paretic limb.

TMS: TMS will be used to both quantify motor cortical excitability (Aim 2 - recruitment curves, short-latency afferent inhibition) and as an intervention (cTBS). TMS will be delivered using our own MagPro X100 with MagOption magnetic stimulator and a 90mm figure-8 coil (MCF-B70, MagVenture Inc.). All stimulation sites will be recorded using the BrainSight™ stereotactic guidance system to reduce variability within and across sessions.

TMS Assessments: Motor evoked potentials (MEPs) will be recorded from the paretic and non-paretic extensor carpi radialis using surface electromyography (PowerLab 8/30 and Bioamplifier, AD Instruments). The extensor carpi radialis was chosen because: 1) most patients with upper hemiparesis present with tonic wrist flexion and 2) the extensor carpi radialis is functionally relevant to the serial targeting task and chosen subtests of the Jebsen Hand Function Test. We have successfully stimulated the extensor carpi radialis in both healthy and clinical populations.

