The statistical approach and power analyses were developed in consultation with the Center for Statistical Consulting and Research at the University of Michigan. For Specific Aim 1 (**Determine whether cTBS over contralesional dorsolateral prefrontal cortex prior to motor practice enhances motor learning post-stroke**) the primary outcome metric will be response time during random reaches. The extent of sensorimotor procedural knowledge will be assessed using an Arm (active-cTBS, sham-cTBS) x Session (Session 2, Session 6) repeated measures ANOVA. The extent of procedural knowledge relating to the larger movement sequence will be assessed using a Arm (active-cTBS, sham-cTBS) x Sequence (Random, Repeated) x Session (Session 2, Session 6) repeated measures ANOVA. As a secondary assessment, the rate of procedural learning will be assessed for each measure by including Sessions 3, 4 and 5 as levels of the factor Session. An Arm (active-cTBS, sham-cTBS) x Session (Session 1, Session 6) repeated measures ANOVA will be used to assess time to complete the Jebsen-Hand Function Test

For Specific Aim 2 (**Determine the effects of cTBS over dorsolateral prefrontal cortex upon motor networks**) two separate sets of analyses will be performed. First, separate Arm (active-cTBS, sham-cTBS) x Hemisphere x Time (Session 1, Session 6) repeated measures ANOVA will be performed to assess change in intracortical motor networks (recruitment curves, short-latency afferent inhibition) across study arm. Motor evoked potential amplitude will be the dependent variable. Arm x Hemisphere x Time interactions will be decomposed using separate Arm x Time repeated measures ANOVAs for each Hemisphere.

Second, to assess changes in intercortical neural networks group level maps for each identified component in the independent component analysis will be assessed using separate Arm x Sequence random-effects analysis for Session 1 and Session 6. Statistical threshold will be set to $p < 0.05$ and corrected for multiple comparisons using the false discovery rate.

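### The Aim 1 Arm x Session crossover test of random-reach time has no period term; adding one is a cheap protection of power if gains differ between the first and second arm

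*Combined protocol and SAP*

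**What the plan says.** Sixteen people each complete an active and a sham arm, with a three-week break between them. Under Design, "The order of each arm will be counterbalanced". The Aim 1 test in Statistical Analyses and Power reads: "The extent of sensorimotor procedural knowledge will be assessed using an Arm (active-cTBS, sham-cTBS) x Session (Session 2, Session 6) repeated measures ANOVA". The factor called Sequence in the neighbouring three-way ANOVA means random versus repeated reaches, not treatment order. No period or order term is named anywhere.

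The Behavioral Test Battery section separates two kinds of material. For the repeated targets, "Different sequences matched for difficulty will be used in each arm". For the random reaches, in Sessions 2 to 5 "of each cross-over arm participants will complete 30 reaches where the targets will occur in a random series", with a further 30 later in the same set, and the same set again in Session 6. Their purpose is clear: "Comparison of response times during random reaches across session will be used to index sensorimotor procedural knowledge".

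Other two-way tests have the same form. For the Jebsen test, "An Arm (active-cTBS, sham-cTBS) x Session (Session 1, Session 6) repeated measures ANOVA will be used to assess time to complete" it, and the TMS measures get Arm x Time ANOVAs within each hemisphere. Potential Problems and Alternative Strategies offers a mixed model as an option if patients are lost between arms, and lists no terms for it.

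The plan names two primary measures for Aim 1. The Behavioral Test Battery names total time to complete the sequence; the analysis section names random-reach response time. These passages must be reconciled. This point follows the analysis section.

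**The concern.** The outcome is learning. From the Behavioral Test Battery, one arm supplies 4 x (120 + 270) + 120 = 1,680 reaches, of which 5 x 60 = 300 are random, all before the second arm starts. The new target sequence does not make random reaching new again. A smaller or otherwise different gain in the second arm is therefore plausible, although the documents neither state it nor give a size.

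A retained shift in level does no harm, because the starting session is measured again in each arm and the shift cancels in the change score. Only a difference in gain matters. Counterbalancing stops such a difference from biasing the comparison when completers are balanced by order, but it leaves the difference in the error term. When completers are not balanced, part of it also enters the estimate. At stake are power with 16 participants and, after uneven loss, the estimate in the trial at hand.

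**Working it through.** **Plan's own figure.** The sample-size passage gives 5 to 12 participants for 80% power at alpha 0.05 with correlation 0.7. With f² = η²/(1-η²), noncentrality f²Nm/(1-0.7) and m = 6 repeated measurements (m is not stated), η² = 0.06 gives N = 12 and η² = 0.16 gives N = 5, so the range reproduces. It makes no mention of a period difference.

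**Set-up.** In a 2 x 2 within-person layout the Arm x Session test is a one-sample t test on W = (active change) - (sham change), with change = Session 6 minus Session 2. Scale W to SD 1 within order group. Let τ be the true effect and d the first-arm minus second-arm difference in gain. Then:
- active first: mean of W = τ + d
- sham first: mean of W = τ - d

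Inputs from the documents: n = 16, counterbalanced (8/8 if all complete), alpha 0.05. Assumptions: d from 0 to 1 SD; τ = 0.75 SD, chosen because it gives 80% power at n = 16; and τ = 0.4 SD as a smaller alternative. One reading of the plan's partial η² of 0.135 is f = √(0.135/0.865) = 0.39, but the plan does not say how its effect sizes map to this contrast.

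**Without period:** mean of all W, n-1 df. **With period:** mean of the two order-group means, pooled within-order SD, standard error 0.5√(1/n1 + 1/n2), n-2 df.

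**Balanced completers, 8/8.** Both estimates equal τ on average, and their true standard error is 0.25. Without period, the estimated error variance rises by the factor 1 + d² x 16/15. At d = 0.5 this is 1.27, a standard error √1.27 = 1.13 times too large; at d = 1 it is 2.07, or 1.44 times. Simulated rejection rates (400,000 trials per cell):

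| d | Power, τ=0.75, without/with | Power, τ=0.4, without/with | Type I error without |
|---|---|---|---|
| 0 | 80/80% | 32/32% | 5.0% |
| 0.25 | 78/80% | 30/32% | 4.4% |
| 0.5 | 72/80% | 24/32% | 2.9% |
| 1 | 49/80% | 10/32% | 0.6% |

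With period, type I error stays at 5.0%.

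**Unbalanced completers.** Without period the estimate is shifted by d(n1-n2)/(n1+n2); with period the shift is 0. For d = 0.5:
- 8/7: 0.5 x 1/15 = 0.03 SD
- 8/6: 0.5 x 2/14 = 0.07 SD
- 8/4: 0.5 x 4/12 = 0.17 SD

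At τ = 0.75 and d = ±0.5, power without period is 73% or 56% at 8/6, depending on the sign of d, against 72% with period. At 8/4 it is 76% or 37%, against 60%. Type I error without period never exceeded about 5.6%.

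**How often splits arise.** If 2 of 16 leave at random from 8/8, the chance of an 8/6 split is 2 x C(8,2)/C(16,2) = 56/120 = 47%. If 4 leave, the orders differ by 2 or more in 57% of cases and split 8/4 in 8%. The documents give no loss rate.

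**Price of adjusting when d = 0 (τ = 0.75).** Power falls from 80.1% to 79.7% at 8/8, 77.1% to 76.4% at 8/7, 73.6% to 72.1% at 8/6 and 66% to 60% at 8/4. The adjusted estimate has the larger mean squared error when |d| is below its own standard error: 0.26 at 8/7, 0.27 at 8/6 and 0.31 at 8/4. At 8/4, mean squared error without/with is 0.083/0.094 at d = 0 and 0.111/0.094 at d = 0.5.

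**The case against.** The strongest reply is that the harm rests on a quantity found nowhere in the documents. At d = 0.25 the power loss is only 2 points, and the large losses need a practice gap comparable with the assumed treatment effect. The 80% baseline is itself an assumption. At 8/6 with d = 0.5 the shift of 0.07 SD is about a quarter of a standard error (0.27). All of this stands, and it is why the point is a cheap improvement and not a flaw that undermines the trial.

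A second reply is that the plan already has counterbalancing, a washout, new sequences and a fallback mixed model. Counterbalancing removes bias only among balanced completers and does not restore power. The washout is aimed at carryover. The new sequences leave the random blocks unchanged. The mixed model is optional, applies only after loss and has no listed terms: a gap in specification, though not evidence that the unadjusted ANOVA would be used in that case.

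A reader might infer more than the documents support:
- **That the cTBS estimate is biased in general.** It is not at 8/8. After loss unrelated to order the shift is specific to the trial at hand and averages to zero; the plan foresees loss but does not say that it differs by order.
- **That false positives are inflated.** The balanced test is conservative, and the unbalanced one barely exceeds 5%.
- **That the same holds for the Sequence and Hemisphere interactions.** There, a period difference common to both levels cancels.
- **That it holds equally for the secondary measures.** For Jebsen the plan says "To minimize learning effects each item will be tested 5 times but only the last two times will be used", which weakens the concern, and for the TMS measures no practice mechanism is documented.
- **That it holds equally for total sequence time.** If that is the intended primary measure, the mechanism is weaker, because the sequence is new in each arm.

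**Conclusion.** The point holds as a low-cost improvement. The Aim 1 Arm x Session test has no period term, and the plan supplies none elsewhere. If first-arm and second-arm gains differ by 0.5 SD, the balanced test loses about 8 power points at either assumed effect (80% to 72%, or 32% to 24%); at 0.25 SD it loses about 2. If completers split 8/6 or 8/4, a 0.5 SD gap moves that trial's estimate by 0.07 or 0.17 SD. These sizes depend on the assumed d and τ and on normal, equal-variance changes. The absence of the term, the formula for the shift and the small price of adjusting at 8/8 do not depend on the size of d.

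**What to change.** In Statistical Analyses and Power, define the Aim 1 test of the active-minus-sham difference in change (Session 6 minus Session 2) as the mean of the two order-group means of each person's active-minus-sham change, with pooled within-order variance and n-2 df (14 at 8/8). Equivalently, add order group as a between-subject factor to the ANOVA and test Arm x Session with the order groups equally weighted. Apply the same contrast secondarily to Jebsen and to the per-hemisphere TMS Arm x Time tests, using Session 6 minus Session 1. Reconcile the two statements of the primary measure.

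If the mixed model is used to include one-arm completers, fit fixed arm and period to the per-period change score. In complete data it gives the same point estimate as the contrast when the participant variance is estimated above zero. When that variance is estimated at zero, the standard error and df can differ. In simulation this happened in about 49% of datasets if gains are uncorrelated between arms and in 12-16% at a correlation of 0.3. Keep the contrast as the primary test.

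The cost is wording and one error df, with no new data. If d = 0, power falls by about 0.4 points at 8/8, 0.7 at 8/7, 1.5 at 8/6 and 6 at 8/4, and with unbalanced completers mean squared error is somewhat larger for d below about 0.26-0.31 SD. The term adjusts for period differences only; it does not correct unequal carryover.

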Targeted enrollment for Aim 1 (Behavior) and Aim 2 (Motor networks) is 16 participants. This number was derived using effect sizes from our previous work. We observed effect sizes (partial η^2) for two-way repeated measures Stimulation Site x Session interactions of 0.135 (M1-cTBS vs. Control) and 0.107 (S1-cTBS vs. Control) when comparing response time from early practice to a delayed retention test. Brodie et al. observed effect sizes for motor and sensory improvements pre- to post an S1-5Hz repetitive TMS intervention that ranged between medium (partial $\eta^2 = 0.06$) to large (partial $\eta^2 > 0.16$). Based upon these effect sizes, the targeted enrollment that provides a power of 0.80 at an alpha level of 0.05 with a correlation of 0.7 among the repeated measures is between 5 and 12 participants (G*Power). These numbers are consistent with previously published work using similar cross-over designs to investigate the efficacy of M1 non-invasive brain stimulation interventions upon both behavior and M1 physiology post-stroke (i.e. recruitment curves and short-latency- afferent inhibition). In these studies sample sizes range from 6-16 stroke patients. To

Study Title: Modulating interaction of motor learning networks in rehabilitation of stroke

account for effect sizes within the lower range of our estimates, overestimates of the correlations between the different levels in our repeated measures design as well as experimental mortality (see **Potential Problems and Alternative Strategies**), we will target 16 individuals.

With respect to the measures of resting state functional connectivity (Aim 2), the majority of work post-stroke has been aimed at determining differences in network functional connectivity compared to non-stroke control individuals. To our knowledge, no studies have assessed changes in resting state connectivity across an intervention similar to that proposed here. The closest approximation is a longitudinal study looking at functional connectivity between ipsilesional and contralesional M1 post-stroke. This study (n=12 patients) demonstrated significant differences between 1, 3 and 6 months post-stroke. Therefore, 16 individuals should be sufficient to detect any changes in functional connectivity associated with our intervention.

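### The Aim 1 Arm x Session test fixes the baseline slope at 1; estimating that slope is a cheap gain in precision, of a size that depends on correlations the plan does not give

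*Combined protocol and SAP*

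**What the plan says.** In Statistical Analyses and Power, the Aim 1 paragraph states that "the primary outcome metric will be response time during random reaches" and tests it with an "Arm (active-cTBS, sham-cTBS) x Session (Session 2, Session 6) repeated measures ANOVA". The Jebsen test is handled in the same way: "An Arm (active-cTBS, sham-cTBS) x Session (Session 1, Session 6) repeated measures ANOVA will be used".

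Under Design, participants "will serve as their own matched control in a cross-over design", and "The order of each arm will be counterbalanced". Under Behavioral Test Battery, in Sessions 2 to 5 "participants will receive either active or sham cTBS over dorsolateral prefrontal cortex following the initial set of 120 reaches". The Session 2 test reaches therefore precede all stimulation in that arm.

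The sample size paragraph assumes a power of 0.80 at alpha 0.05 "with a correlation of 0.7 among the repeated measures", arrives at 5 to 12 participants, and targets 16. Among its reasons for the margin it lists "overestimates of the correlations between the different levels in our repeated measures design".

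No section uses the Session 2 value as a covariate. Potential Problems and Alternative Strategies mentions a mixed effect model only as an option after dropout between arms, and names no baseline term.

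**The concern.** The crossover already removes each participant's general level, because active and sham are compared within the person. Subtracting both Session 2 values as well brings in the noise of two more measurements. That is worthwhile only if the Session 2 arm difference predicts the Session 6 arm difference strongly. If it predicts weakly, a slope of 1 is too large and the subtraction mostly adds variance. In a 16-person trial, precision that could be had from data already collected is worth keeping.

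**Working it through.** **The plan's own figure.** The G*Power repeated-measures formula is lambda = f^2 x N x m/(1 - rho), with f^2 = eta^2/(1 - eta^2). For partial eta^2 = 0.107, f^2 = 0.107/0.893 = 0.120. With m = 2 and rho = 0.7, N = 12 gives lambda = 0.120 x 12 x 2/0.3 = 9.6 and power just above 0.80; N = 11 falls short. The upper end of 5 to 12 is thus reproduced. The lower end is within reach under other settings (m = 4 gives 6 at eta^2 = 0.16 and 5 at 0.20), but the plan does not state its settings.

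**What the planned test is.** The interaction F(1,15) is the square of the paired t on (S6 - S2) active minus (S6 - S2) sham, which is D6 - 1 x D2.

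**Variances.** Let rw be the correlation between sessions within an arm, rb between arms at the same session, and rx between arms across sessions.
- Var(D6) = Var(D2) = 2 sigma^2 (1 - rb)
- Cov(D6, D2) = 2 sigma^2 (rw - rx), so b = (rw - rx)/(1 - rb)
- Planned contrast: 4 sigma^2 (1 - rb)(1 - b)
- D6 adjusted for D2: 2 sigma^2 (1 - rb)(1 - b^2)
- Ratio: 2/(1 + b)

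**If every pair has correlation 0.7 (assumed).** Then b = 0. The planned variance is 4 x 0.3 = 1.2 sigma^2 and the adjusted variance is 2 x 0.3 = 0.6 sigma^2, a ratio of 2. At n = 16 the standard errors are sqrt(1.2/16) = 0.274 sigma and sqrt(0.6/16) = 0.194 sigma. Estimating the slope raises 0.6 to about 0.6 x (1 + 1/13) = 0.646 sigma^2. The ratio achieved is then 1.2/0.646 = 1.86, and the share of the loss recovered is (1.2 - 0.646)/0.6 = 92%. With order also in the model, the simulated standard error is 0.202 sigma. At b = 0 the covariate itself explains nothing; the gain comes from no longer subtracting it.

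**Other values of b.** Simulation at n = 16, two-sided 0.05, with the effect set at each b to 0.749 standard deviations of the planned contrast, so that the planned test has 80% power:

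| b | Variance ratio 2/(1+b) | Power, planned | Power, slope estimated |
|---|---|---|---|
| 0 | 2.00 | 80% | 96% |
| 0.3 | 1.54 | 80% | 91% |
| 0.5 | 1.33 | 80% | 87% |
| 0.8 | 1.11 | 80% | 80% |

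Type I error of the regression stays close to 5%. At b = 0.8 the cost of estimating the slope and the lost degrees of freedom use up the gain.

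**Carry-over.** Suppose a share c of the active gain persists through the whole of Arm 2. In participants who had active first, both D2 and D6 fall by c times the effect. Averaged over the two orders, the regression intercept is the effect times 1 - (1 - b)c/2, while the change score stays unbiased. For b from 0 to 0.5:

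| c | Power, planned | Power, slope estimated |
|---|---|---|
| 0.25 | 80% | 82-90% |
| 0.5 | 80% | 76-78% |
| 1 | 80% | 39-59% |

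**Coding of order.** With order coded 0/1, the intercept is the cTBS effect in one order group only, so it also carries the period effect. With no cTBS effect, an assumed period effect of 0.5 sigma and b = 0, type I error was 32%. With +1/-1 coding and equal numbers per order, the period effect drops out of the intercept.

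**The case against.** The strongest reply is that subtracting each arm's own baseline is a deliberate guard. The outcome is learning, the protocol describes the three-week break as minimising carry-over and as a trade-off against losing participants, and a level shift left from Arm 1 is removed completely by the change score. This stands as a real cost: as the carry-over table shows, the regression already has slightly lower power at c = 0.5. It does not defeat the proposal, because the plan's working premise is that the break keeps carry-over small, and the planned contrast can be kept beside the regression.

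A second reply also stands. A reader might infer that the plan's own 0.7 proves a doubling of variance. It does not. The plan gives one G*Power input, not a four-cell correlation matrix, and N = 12 is reproduced with m = 2, where only one correlation enters. Sessions within an arm fall inside three weeks, while the arms are separated by a break and use different sequences. Correlation may therefore be higher within an arm than across arms, which makes b positive and the gain smaller. If the cross-arm correlations stay at 0.7 and the within-arm correlation is 0.8 (assumed), b = 0.1/0.3 = 0.33 and the ratio is 1.50; at 0.9, b = 0.67 and the ratio is 1.20.

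A reader might also infer that the planned test is biased or that the sample size is wrong. Neither follows. The interaction test is valid, and the study was sized on interaction effects. With m = 2 and partial eta^2 = 0.107, the plan's method gives about 92% power at n = 16.

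**Conclusion.** The point holds as a cheap improvement in efficiency. For b between 0 and 0.8 and little carry-over, the regression is at least as powerful as the planned test: 16 points better at b = 0 (96% against 80%) and level by b = 0.8. The doubling of variance is the upper end for b at or above 0 and rests on equal correlations, which the documents do not establish. The regression loses its advantage if about half or more of the active gain persists through Arm 2. No stated figure is shown to be wrong. For the Jebsen test the structure is the same, but the documents give no correlation for it, so no size of gain can be stated.

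**What to change.** Before data are seen, prespecify the primary Aim 1 analysis as follows.

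- Regress each participant's Session 6 active-minus-sham difference in random-reach response time on the Session 2 active-minus-sham difference, plus order coded +1/-1 (not 0/1). The intercept is the cTBS effect.
- If a mixed model is preferred, the baseline slope must be estimated within patients, with patient as a fixed block or baseline differences as the covariate. A random-intercept model with one common slope on raw Session 2 values mixes in the between-patient slope. Under equal correlations of 0.7 it leaves about 0.86 sigma^2 and so recovers only (1.2 - 0.86)/0.6, about 56%, of the loss.
- Keep the Arm x Session contrast as a prespecified sensitivity analysis. It is the estimate less exposed to persisting carry-over, so a marked difference between the two should be reported and discussed.
- The same form may be used for the Jebsen test, with Session 1 as the baseline.

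The cost is analysis wording, one or two degrees of freedom, and more reliance on the three-week break. No extra participant, visit or measurement is needed.
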